Therapy Phase Visits 2, 3 & 4 (week 1, 4, 8 respectively; + 7 days) – Treatment and Control subjects will be assessed for adverse events and changes to concomitant medications. Obtain BP and weight. Administer the TFEQ-R18V2 Questionnaire. Collect and review paper diaries, dispense new paper diaries and review instructions for weekly completion. All subjects will be encouraged to follow a healthy 1200 calorie diet throughout the study. Subjects will be instructed to return with their paper diaries at their next scheduled visit.

Treatment subjects will be assessed for any adverse device effects (ADE), T6/T7 dermatome assessment, review and download of diary data, and stimulation adjustment (if needed). Treatment subjects will be discharged with the smartphone application and the Elira wearable patch system and instructions on use. Treatment subjects will be instructed to return with the Elira wearable patch system and smartphone app at their next scheduled visit.

End of Study Visit 5 (week 12; ± 7 days) – Treatment and Control subjects will be assessed for adverse events and changes to concomitant medications. Physical including weight, BP, requisition for laboratory tests, urine pregnancy test for WOCBP, and completion of questionnaires (PHQ9, TFEQ-R18V2, and Patient Preference Survey). Collect and review paper diaries.

Treatment subjects will return the Elira wearable patch system and the smartphone application. Treatment subjects will be assessed for ADEs and have their T6/T7 dermatome area examined.

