#### 6.1.3 Secondary Effectiveness Endpoints:

- Number of subjects reporting >5% total body weight loss at the end of Therapy as compared to Baseline between Treatment and Control
- Percent change in appetite scores at the end of Therapy Period compared to Baseline between Treatment and Control.
- Blood pressure, blood lipids, ALT and HbA1c at the end of Therapy Period as compared to Baseline between Treatment and Control groups.
- % changes in BMI at the end of Therapy Period compared to Baseline between Treatment and Control groups

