#### 8.2 JUSTIFICATION OF SAMPLE SIZE

The calculated sample size for the study is based on conservative imputation of results from other studies on weight loss including the use of TENS for weight loss. The degree of coaching/dietary support throughout the present study is moderate intensity lifestyle/weight coaching. The sample size modeling assumes an average of 3.5% TBWL in Control subjects using diet and exercise alone. The estimated weight loss in the Treatment subjects is modeled from preliminary data on T6/T7 dermatomal TENS when used for weight loss: 7.5% TBWL. The variance of the responses in the study (i.e. Standard Deviation) was modeled at + 5% TBWL. This value was taken from previous dermatomal TENS weight loss study results. The model assumes a 30% drop out rate across groups and an 80% powered endpoint using an adaptive p spending model wherein interim posterior probability assessments are allowed after enrolling proscribe cohorts of not less than 25 subjects per group for not less than 7 weeks of stimulation. The alpha penalty will be minimized per interim by assessing the relationship between stimulation (i.e. dose) and weight loss using Normalized Linear Dynamic Modeling (NLDM) to determine overall sample size projected (i.e. futility) rather than assessing the primary endpoint hypothesis per se. Monotonicity will not be assumed in this analysis. This modeling provides an estimate of 75 subjects per group, for a total study size of 150 subjects. However, the protocol allows for enrollment of additional subjects should the interim model project under powering of the primary endpoint.

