#### 8.3 RETENTION AND HANDLING OF MISSING DATA

Every effort will be made to collect all data at each time point in the study. The PI and the Clinical Data Monitor will minimize the amount of missing data by appropriate management of the prospective clinical trial, proper screening of subjects, and training of clinicians. If a subject misses a dietary entry into either the paper or electronic diary, a look back entry for that value is allowed provide for the week preceding the event. Outside this window, data will be considered missing. All partial data available for subjects who drop out during the course of the study will be included.

For missing data imputation, the last value carried forward method will be utilized. To assess the potential effect of missing data on the primary effectiveness endpoint, the following sensitivity analyses will be performed to impute missing values.

Sensitivity Analyses: First, the primary effectiveness endpoint will be assessed with all missing data points imputed as failures for both groups. Second, the primary efficacy endpoint will be assessed with all missing data points imputed as successes for both groups.

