### 18.6 APPENDIX 6: SCHEDULE OF EVENTS

[figure not shown]
STUDY PERIOD	SCREENING/ BASELINE	ENROLLMENT/ RANDOMIZATION		END OF STUDY 		
VISIT #	VISIT 0	Visit 1	VISIT 2	VISIT 3	VISIT 4	VISIT 5
WEEK#	-1 WEEK	WEEK 0	WEEK 1	WEEK 4	WEEK 8	WEEK 12
VISIT WINDOW 	±7 Days	±7 Days	±7 Days	±7 Days	±7 Days	±7 Days
Informed Consent	Х					
Inclusion/Exclusion Criteria	Х	х				
Medical History	Х					
Diet History	Х					
Physical Exam	Х					Х
T6/T7 dermatome assessment	X 	X 	X 	X 	X 	X 
Blood Pressure	Х	х	х	х	Х	Х
Concomitant Medication Review	Х	х	Х	х	Х	Х
Height	Х					
Weight	Х	х	х	х	Х	Х
Laboratory Requisition - Blood Tests 	Х					Х
Urine Pregnancy Test (WOCBP)	Х	X e				Х
Administration of Patient Preference Survey	Х					Х
Administration of PHQ-9	Х					Х
Administration of TFEQ-R18V2		х	х	х	Х	Х
Provide/Train on Paper Diaries 	Х	х	х	х	Х	
Collect and Review Paper Diaries 		х	х	х	Х	Х
Randomization 		х				
Encourage 1200 calorie diet		х	х	х	Х	
Provide Electronic Scale		х				
Provide and Train on Electronic Diary 		х	х	х	Х	
Collect and Review Electronic Diary 			х	х	Х	Х
Provide and Train on TENS Unit and Patches 		x	x	х	х	
Collect and Examine TENS Unit and Patches 			х	х	х	Х
Provide/Instruct on TENS Clean-Cote Skin Wipes and/or Alcohol Prep Pads 		х	х	х	х	
Provide/Instruct on Cetaphil Lotion 		х	Х	х	Х	
Assessment of Adverse Events	Х	х	Х	х	Х	Х
Assessment of Adverse Device Effects 		х	Х	х	Х	Х
Schedule next visit	Х	х	Х	х	Х	
Study Exit						Х

All visits are ± 7 days
 Blood tests include HbA1c, lipid panel, CMP
 To be completed for control and treatment group

 To be completed for treatment group only 5 – Randomization into control or treatment group

 Complete UPT only if not completed at screening
7 – Complete all procedures at End of Study or Early Termination Visit

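### HbA1c, lipids and ALT have no draw between screening and exit, so unrestricted carry-forward scores a dropout with no exit draw as zero change; this biases the arm difference and makes its interval too narrow

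*Combined protocol and SAP*

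**What the plan says.** - **Endpoints.** Section 6.1.3 compares the arms on "Blood pressure, blood lipids, ALT and HbA1c at the end of Therapy Period as compared to Baseline between Treatment and Control groups".
- **Draw times.** In the Appendix 6 schedule, the row "Laboratory Requisition - Blood Tests" is marked at Visit 0 and Visit 5 only. Its footnote reads "Blood tests include HbA1c, lipid panel, CMP"; ALT is part of the CMP. The Visit Schedule in the Protocol Summary agrees: laboratory tests appear in the exit visit ("Physical including weight, BP, requisition for laboratory tests, urine pregnancy test for WOCBP, and completion of questionnaires") and not in Visits 2 to 4.
- **Early leavers.** Footnote 7 of the schedule says "Complete all procedures at End of Study or Early Termination Visit", so a dropout who attends that visit should have a draw. Section 7.3 also recognises subjects who are lost to follow-up.
- **Missing data.** Section 8.3: "For missing data imputation, the last value carried forward method will be utilized". The sentence is not limited to any endpoint or to post-baseline values. The sensitivity analyses that follow are introduced with "To assess the potential effect of missing data on the primary effectiveness endpoint"; none is given for the laboratory endpoints.
- **Analysis set.** Section 8.4 analyses secondary endpoints on mITT (subjects who initiated therapy), and also on completers.
- **Dropout.** Section 8.2: "The model assumes a 30% drop out rate across groups".

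**The concern.** Weight and blood pressure are taken at every scheduled visit, so carry-forward usually has a post-baseline value to use. The laboratory endpoints have none between screening and exit. For an mITT subject without an exit draw, the last value is the screening value, and the change from baseline is zero by construction. A subject who leaves early and does attend the termination visit has the opposite problem: a draw from, say, Week 2 becomes the end-of-therapy value, because nothing says how such a draw is to be used.

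The invented zeros move each arm mean towards zero and are then counted as real observations, so the standard error is too small as well. Both arms diet, so both may improve. If one arm loses more subjects, that arm looks worse for a reason unrelated to the device. At stake are the estimates and intervals for the metabolic secondary endpoints.

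**Working it through.** **The plan's own figure.** The plan states no effect, SD or power for HbA1c, lipids or ALT, so there is no laboratory figure to reproduce. Its 75 per group is for weight loss. A 4-point difference with SD 5, two-sided 5% and 80% power needs 25 per arm, or 36 after 30% dropout. The larger number may come from the adaptive spending model, whose details are not given. I take 75 per arm as an input only; whether it is right does not affect this point.

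**Inputs from the documents.** 75 per arm and 30% dropout (8.2); 95% two-sided intervals (section 8).

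**Assumptions.** Changes are in units of the SD of change (SD = 1), with improvement positive. Missingness is completely at random. The target is the difference had everyone given an exit draw. The share of dropouts without a draw is unknown and is varied.

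**Formulas.** For an arm with true mean change m and missing share d, after zeros are inserted:

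- mean = (1 − d)m
- variance = (1 − d) + d(1 − d)m²
- SE of the difference = √[(variance_T + variance_C)/75]
- SE from observed values only = √[1/(75(1 − d_T)) + 1/(75(1 − d_C))]

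**Equal missingness, worked case: 1.0 vs 0.5 SD, d = 0.30.**

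- Difference = 0.70 − 0.35 = 0.35, against a true 0.50.
- Variances = 0.70 + 0.21 × 1 = 0.91 and 0.70 + 0.21 × 0.25 = 0.7525.
- SE = √(1.6625/75) = 0.149, against √(2/52.5) = 0.195 from observed values, so the interval is about 24% narrower.
- Bias/SE = −0.15/0.149 = −1.01. With critical value 1.976, coverage is about 83%.
- Test statistic = 0.35/0.149 = 2.35, against 0.50/0.195 = 2.56. Power is about 65% against 72%.

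**Range, equal missingness** (formula checked by simulation; they agree within about half a percentage point):

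| True changes (SD) | Missing per arm | Difference × | SE ÷ observed-value SE | Coverage |
|---|---|---|---|---|
| 0.3 vs 0.1 | 30% | 0.70 | 0.71 | 93% |
| 0.8 vs 0.4 | 30% | 0.70 | 0.74 | 87% |
| 1.0 vs 0.5 | 30% | 0.70 | 0.76 | 83% |
| 1.0 vs 0.5 | 20% | 0.80 | 0.85 | 90% |
| 1.0 vs 0.5 | 10% | 0.90 | 0.93 | about 94% |

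**Unequal missingness.** The estimated difference is the true difference minus (d_T·m_T − d_C·m_C). It shrinks when d_T·m_T exceeds d_C·m_C and grows otherwise. At 0.8 vs 0.4 SD with 15% missing on treatment and 45% on control, it is 0.40 − (0.12 − 0.18) = 0.46, a 1.15-fold inflation.

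With no device effect and a common change of 0.5 SD, 40% vs 20% missing creates a difference of 0.5 × 0.20 = 0.10 SD against the arm with more missing draws. The SE is √[(0.66 + 0.84)/75] = 0.141, and the false-positive rate is about 11%. At 35% vs 25% it is about 6%; at 30% vs 30% it is 5%. With a common change of 0.2 SD, 40% vs 20% gives about 6%.

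**The case against.** Several parts of the other side's case stand.

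- **Baseline carry-forward is not spelled out.** Section 8.3 never says in terms that a baseline value may be carried. But nothing bars it, and for these subjects no other value exists, so following the sentence as written produces the zero.
- **A completer analysis is planned.** Section 8.4 includes secondary endpoints in it, and it inserts no zeros. It is additional to mITT and carries its own selection risk, so it does not repair the mITT result. The multiple-imputation wording in section 8 is permissive, belongs to the Bayesian efficacy analyses and is not tied to laboratory values.
- **30% is the upper end.** It requires that no dropout attends the termination visit, and subjects who never initiated therapy are outside mITT.
- **The target is assumed.** If dropouts drift back towards baseline, zero is less wrong than the coverage figures suggest. The false narrowness remains.
- **These are unpowered secondary measures,** with no success criterion attached.

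Three stronger readings are tempting and not supported. A reader might infer that every dropout is scored as zero; footnote 7 contradicts that for those who attend a termination visit. A reader might infer that the rule always hides a benefit; that needs roughly balanced dropout, and higher control dropout can create one. A reader might infer a generally raised false-positive rate; 8.2 assumes 30% across groups, no imbalance is stated anywhere, and with equal dropout the rate stays at 5%.

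**Conclusion.** The point holds in limited form. The zero-change scoring follows from the schedule, 8.3 and 8.4 read together, for mITT subjects without an exit draw. With roughly equal missing share d, the arm difference is multiplied by (1 − d) and its interval is too narrow compared with observed values. The damage is mainly to the estimate and interval; the test changes little.

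The coverage loss runs from negligible to serious depending on two things the documents do not give: how many dropouts lack an exit draw, and how large the laboratory changes are. If the changes are modest or most dropouts attend a termination visit, little is lost. Unequal dropout is possible because the trial is open label and only one arm receives the device; the direction of any bias then depends on which arm loses more. The change is worth making because it is cheap and the present text offers no check on these endpoints in the mITT set.

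**What to change.** Add a paragraph to section 8.3, for example:

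> For HbA1c, lipids and ALT a screening value is never carried forward as the end-of-therapy value. Missing Week 12 values are multiply imputed by arm from the baseline laboratory value and the available visit weights. An early termination draw enters as an auxiliary value at its own week, not as the Week 12 value. Two supportive analyses are reported: a sensitivity analysis that imputes less favourable values for dropouts (for example, return towards baseline, with proper variance), and an analysis of observed values.

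The sensitivity analysis matters because imputation by arm assumes that dropouts resemble similar subjects who stayed, which may flatter both arms.

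The cost is one paragraph and modest programming; irregular termination draws and subjects with few interim weights need some care. Intervals will be wider than under carry-forward. No new visits, draws or subjects are needed.

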#### 6.1.4 Ancillary Endpoints:

#### Changes between the following values:

- Ease of use/prevalence of use errors associated with the patch unit and dietary application during initial training.
- Subject preference scores at the end of Therapy Period compared to Baseline between Treatment and Control groups.

#### 6.2 ENDPOINT DEFINITIONS & RECORDING METHODS

Endpoint data in hunger, appetite, and dietary compliance are obtained from subject reported assessments (Appendix 4, 5). That is, the measurement of success is based on the subject's report of the parameter using validated tools where available.

Primary source data will be paper based, with each subject receiving diary worksheets to record responses. Treatment subjects will also be assigned an Android Smart Phone onto which has been loaded a copy of custom dietary application (Appendix 5). Subjects will be trained on the use of these tools and assessed for accurate use prior to taking them home. To ensure data privacy, the network interface card (i.e. SIM card) for the phone will be removed such that data can only be downloaded *via* a direct USB link.

#### 7. STUDY POPULATION

#### 7.1 INCLUSION CRITERIA

- **7.1.1** Subject is between 18 65 years of age inclusive.
- **7.1.2** Subject has a BMI of 25-35 kg/ m^2 inclusive.
- **7.1.3** Subject has signed the informed consent form and is able to comply with study protocol and adhere to study visit schedule.
- **7.1.4** Subject is able to wear and use a wearable, patch TENS system.
- **7.1.5** Subject is able to use a touch screen hand held smart phone.
- **7.1.6** Subject is fluent in English and can complete questionnaires.
- **7.1.7** Subject can comply with a 1200 calorie diet for the duration of the study.
- **7.1.8** Females of childbearing potential (FOCBP) must have a negative urine pregnancy test at screening or enrollment visit, prior to placement of ELIRA device.
- **7.1.9** Subject is male or non-pregnant, non-lactating female, who agrees to use effective contraceptive methods throughout the length of the trial based on PI approval.

#### 7.2 EXCLUSION CRITERIA

**7.2.1** Subject has any known gastrointestinal disorder that in the opinion of the PI precludes enrollment into the trial.

- **7.2.2** Subject has had a prior bariatric procedure or any previous procedure on the stomach.
- 7.2.3 Subject has any significant multisystem disease in the opinion of the PI.
- **7.2.4** Subject has > 6.5 HbA1c.
- **7.2.5** Subject has significant cardiac arrhythmia, ectopy, or significant cardiovascular disease.
- **7.2.6** Subject has an existing implanted electrical stimulator (e.g., pacemaker, AICD).
- **7.2.7** Subject is a female of child-bearing potential who is pregnant or intends to become pregnant during the trial period.
- **7.2.8** Subject has current and/or a history of cancer within the past 5 years (not including basal cell carcinoma or cervical carcinoma in situ).
- **7.2.9** Subject has had a weight change of + 5% of his/her Total Body Weight in the 3 months prior to screening.
- **7.2.10** Subject has a moderate / severe psychiatric disorder.
- **7.2.11** Subject has a diagnosed neurological disease.
- **7.2.12** Subject has a diagnosed eating disorder.
- **7.2.13** Subject has a skin disorder affecting the thoracic dermatomes.
- **7.2.14** Subject has active or has ever had shingles in the abdominal area.
- **7.2.15** Subject has abdominal surgery or other scars which may interfere with TENS stimulation in the opinion of the PI.
- **7.2.16** Subject is currently enrolled in other potentially confounding research.
- **7.2.17** Subject has known allergic reaction to materials in the TENS electrodes and/or is otherwise unable to tolerate stimulation with the wearable TENS system.
- **7.2.18** Subject is actively participating or unwilling to discontinue participation in another weight loss program.
- **7.2.19** Subject is taking weight loss control medications including but not limited to OTC medications, Metformin, and Belvig.
- **7.2.20** Subject is unable to take anti-nausea medications planned for the study.
- **7.2.21** Inability to walk at least 0.8 kilometers per day (10 minutes of continuous walking).
- **7.2.22** Current smoker or user of nicotine product or smoking cessation within 1 year of the screening date.
- **7.2.23** History of treatment for or current abuse of drug or alcohol.

**7.2.24**A score of ≥10 on the Patient Health Questionnaire 9 (PHQ-9), demonstrating moderate depression.

- **7.2.25** Any subject that the investigator considers inappropriate for the study for medical reasons.
- **7.2.26** Subject has a history of moderate/severe migraines or severe headache disorders requiring the treatment of Topiramate.
- **7.2.27** Subject is on drug therapy which may alter antral motility or appetite, per PI discretion. (Appendix 8)

#### 7.3 SELECTION AND ENROLLMENT OF SUBJECTS

Prospective study subjects will be screened for study eligibility. A subject is considered enrolled after:

- 1. Written Informed Consent is obtained.
- 2. Meeting all inclusion and exclusion criteria and randomized into the study.
- 3. This study will utilize unique subject numbers for the purpose of trial data collection. Subjects signing an Informed Consent but not meeting all criteria will not be considered enrolled in the study but the signed Informed Consents will be maintained by the PI for seven (7) years.

Following enrollment, subjects should remain in the study until completion of the required Therapy Phase.

A subject's participation may be discontinued for the following reasons:

- Subject Withdrawal: As subject participation in a clinical trial is voluntary, the subject may choose to discontinue participation at any time without penalty or loss of benefits.
- Investigator Termination: The Investigator may terminate the subject's participation without regard to the subject's consent if the Investigator believes termination is medically necessary.
- Lost-to-Follow-up: A subject is lost-to-follow up if he/she does not complete required follow-up, but has not "officially" withdrawn consent. In order to consider a subject lost to follow-up, site personnel should make all reasonable efforts to locate and communicate with the subject. A minimum of three (3) attempts to contact the subject should be recorded in the source documentation including date, time and name of site personnel attempting to make contact.

### 8. STATISTICAL CONSIDERATIONS AND ANALYSIS PLAN

Categorical variables will be summarized by number and percent. Continuous variables will be summarized by total number (N), mean, standard deviation (SD), median, minimum and maximum. Ninety-five percent, 2-sided confidence intervals on estimated means and differences in means between treatment and control groups will be calculated. Confidence intervals will be similarly computed for proportions and differences between proportions. In addition, propensity score and sensitivity analyses will be utilized to compare adverse events and/or adverse device effects incidence versus historical control. Wilcoxon signed rank tests, Fisher exact tests, and Pearson Correlations will be utilized to compare changes in baseline variables between varying

time points of the study (e.g. baseline versus post stimulation treatment) and to correlate stimulation parameters with endpoint values. Markov-chain Monte Carlo Analyses will be utilized to conduct Bayesian posterior probability distributions with multiple imputations allowed to assess treatment efficacy within and between cohorts. The need for additional endpoints to achieve primary and secondary significance will be determined utilizing longitudinal modeling. Finally, dose response will be modeled and analyzed within and between cohorts to determine optimal therapy dose for stimulation in open label period within and between cohorts using Normal dynamic linear modeling (NDLM) since monotonicity of the response cannot be assumed.

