## Statistical Analysis

Categorical variables will be summarized by number and percent. Continuous variables will be summarized by total number (N), mean, standard deviation (SD), median, minimum and maximum. Ninety-five percent, 2-sided confidence intervals on estimated means and differences in means between treatment and control groups will be calculated (corrected for multiplicity where needed). Confidence intervals will be similarly computed for proportions and differences between proportions. In addition, propensity score and sensitivity analyses will be utilized to compare adverse events and adverse device effects incidence versus historical control. Wilcoxon signed rank tests, Fisher exact tests, and Pearson Correlations will be utilized to compare changes in baseline variables between varying time points of the study (e.g. Baseline versus Therapy) and to correlate stimulation parameters with endpoint values.

Markov-chain Monte Carlo Analyses will be utilized to conduct Bayesian posterior probability distributions with multiple imputations allowed to assess treatment efficacy within and between cohorts. The need for additional endpoints to achieve primary and secondary significance will be determined utilizing longitudinal modeling. Finally, dose response will be modeled and analyzed within and between cohorts to determine optimal therapy dose for stimulation in open label period within and between cohorts using Normal dynamic linear modeling (NDLM) since monotonicity of the response cannot be assumed.

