#### 5. STUDY DESIGN

Randomized, adaptive parallel arm study. Subjects will be initially screened during a screening period (1 week, ±7 days; Figure 2). During this screening period, prior to study procedures being performed, subjects will sign an informed consent form. Then they will have their

[figure not shown]

Figure 2: Study Outline

weight and blood pressure measured, FOCBP will have a pregnancy test, get blood drawn for analysis (blood lipids, CMP, hemoglobin A1c), and complete patient preference questionnaires. At the end of the screening/baseline period, eligible subjects will be offered the chance to enroll in the study. After enrolling, subjects will be randomized to treatment or control groups.

The Treatment group will be instructed to follow a healthy 1200 calorie diet that they will follow for the duration of the study and will receive training on the use of the weekly paper diary, electronic scale, smartphone app and the Elira wearable patch system. All treatment subjects will be required to stimulate in the office for a period of time to confirm sufficient system training and tolerability of the stimulation. Following this, subjects will enter the Therapy Period, for a 12-week duration.

The Control group will be instructed to follow a healthy 1200 calorie diet that they will follow for the duration of the study and will receive training on the use of the weekly paper diary and electronic scale. The Control group will not receive the electronic smartphone app or the Elira wearable patch system.

At the end of the Therapy Period, subjects will be assessed for weight loss, blood pressure, CMP, blood lipids, HbA1c, and will be terminated from the study.

The study utilizes an adaptive approach where cohorts of enrolled subjects (in groups of 25 per arm) are assessed for dose response and progression to achievement of primary and secondary endpoints. Frequent interim endpoint assessment utilizing Markov-chain Monte Carlo (MCMC) methods coupled with longitudinal analyses will be utilized to determine sample sizes for future cohorts (assessed primarily via Normal dynamic linear modeling [NDLM]).

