#### 6.1.2 Primary Effectiveness Endpoint:

The primary effectiveness endpoint is the percent reduction in total body weight loss (%TBWL), measured as End Weight – Initial Weight divided by Initial Weight, multiplied by 100, at the end of Therapy period compared to Baseline between Treatment and Control.

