#### 8.1.3 Weight Loss

The null and alternative hypotheses are:

$$H_0$$
:  $π_T ≤ π_C$ 
 $H_1$ :  $π_T > π_C$ 

Where  $\pi_T$  and  $\pi_C$  are the probabilities of weight loss (% TBWL, %EBWL) in treatment versus control respectively. Estimates of the proportion of weight loss in pounds, % total body weight loss (%TBWL) Excess Body Weight Loss (%EBWL) or BMI will be compared with a tested Fishers Exact Test. Estimates and 95% confidence intervals will also be computed for the difference in rate of weight loss between varying stimulation levels.

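### The sentence on additional endpoints needed for significance must be replaced: taken literally or as a slip for subjects, it has no stated error control

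*Combined protocol and SAP*

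**What the plan says.** The same sentence stands in Section 8 and in the Statistical Analysis part of the Protocol Summary: "The need for additional endpoints to achieve primary and secondary significance will be determined utilizing longitudinal modeling".

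Section 5 describes the modelling. Cohorts of 25 per arm "are assessed for dose response and progression to achievement of primary and secondary endpoints", and "Frequent interim endpoint assessment utilizing Markov-chain Monte Carlo (MCMC) methods coupled with longitudinal analyses will be utilized to determine sample sizes for future cohorts". Section 5.3 makes the trial open label with no blinding.

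Two places touch on error control:
- In the Summary, the sentence on confidence intervals carries a parenthesis: "will be calculated (corrected for multiplicity where needed". The matching sentence in Section 8 lacks it.
- Section 8.2 says: "The model assumes a 30% drop out rate across groups and an 80% powered endpoint using an adaptive p spending model". It adds that interims project sample size rather than test the primary hypothesis.

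The sample-size row of the Summary says instead that interims assess significance, and that up to 300 subjects may be enrolled if the interim is not significant.

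Section 6.1.2 names one primary effectiveness endpoint, %TBWL. Section 8.1.3 widens the set: "Estimates of the proportion of weight loss in pounds, % total body weight loss (%TBWL) Excess Body Weight Loss (%EBWL) or BMI will be compared". %EBWL is not listed anywhere in 6.1.1 to 6.1.4.

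**The concern.** The sentence names significance as the goal and modelling of trial data as the means. In a trial that the Summary calls pivotal, an endpoint added because accumulating data suggest it will succeed has no valid p-value. If the intended word was *subjects*, a different problem appears: the sample size can be enlarged on interim results, with secondary endpoints among the reasons, and no rule says how the final test allows for this.

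Section 8.5 does not help. It requires deviations from the plan to be documented, but adding an endpoint under this sentence would follow the plan.

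**Working it through.** **1. Which reading is likelier.** Three places use interim modelling to set the number of subjects: the Summary, Section 5 and Section 8.2. None describes choosing, adding or promoting an endpoint. Adding an endpoint also cannot make the existing primary endpoint significant. The slip is therefore the likelier explanation, but the text as printed still grants the literal permission, twice.

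**2. Is either reading covered elsewhere?**

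| Safeguard | Alpha | Method or boundary | Added endpoints | Enlargement to 300 |
|---|---|---|---|---|
| Multiplicity parenthesis (Summary) | no | no | no | no |
| Adaptive p spending (8.2) | no | no | no | no rule given |
| Deviations clause (8.5) | no | no | no | no |

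**3. Inputs.** The plan states no alpha and no family-wise error rate, so there is no figure to reproduce on this point. I assume two-sided 0.05, by analogy with: "Ninety-five percent, 2-sided confidence intervals on estimated means and differences in means between treatment and control groups will be calculated". The numbers of endpoints, the correlations and the timing of looks are also my assumptions, because the plan gives none.

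**4. Literal reading.** Take one planned endpoint plus 1, 3 or 5 added ones, so k = 2, 4 or 6, each tested at 0.05 with no true effect. If independent, the chance of at least one false positive is 1 − 0.95^k:
- k = 2: 1 − 0.9025 = 0.0975
- k = 4: 1 − 0.8145 = 0.1855
- k = 6: 1 − 0.7351 = 0.2649

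For equally correlated normal statistics with correlation ρ, the chance is 1 − E{[Φ((1.96 − √ρ·U)/√(1−ρ)) − Φ((−1.96 − √ρ·U)/√(1−ρ))]^k}, with U standard normal. By numerical integration:

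| Correlation | k = 2 | k = 4 | k = 6 |
|---|---|---|---|
| 0 | 9.8% | 18.5% | 26.5% |
| 0.5 | 9.1% | 15.6% | 20.7% |
| 0.9 | 7.0% | 9.4% | 10.8% |

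**5. Subjects reading.** Suppose the primary endpoint is tested at 150 subjects and, if not significant, again at 300, each time at |Z| > 1.96. The two statistics have correlation √(150/300) = 0.707, and the chance of a false positive at either test is 8.3%. With tests after every 50 subjects up to 300 (six looks, correlation √(i/j) between looks i and j), it is 15.5%.

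**6. What the sample size rests on.** Section 8.2 uses only %TBWL: 3.5% against 7.5%, SD 5%, 80% power and 30% dropout. No secondary endpoint enters, so the mention of secondary significance has no counterpart in the sizing.

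**The case against.** The strongest defence is that this is a drafting slip in a sentence about sample size. Sections 5 and 8.2 and the Summary support that, and 6.1.2 to 6.1.4 list the endpoints with no provision for extension. I accept it as the likelier reading. It does not clear the text, because the corrected sentence would still tie enrolment to secondary significance, and enlargement to 300 would still lack an alpha rule.

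Two stronger inferences are tempting and should not be drawn.
- **That the plan removes error control for the primary endpoint.** A single test of %TBWL at its own alpha is not affected by adding other endpoints. The inflation in step 4 falls on a claim that the trial succeeded on some endpoint, and the plan does not define success that way.
- **That enrolment runs on until secondary endpoints are significant.** The sentence says modelling will determine the need. The Summary puts the maximum at 300, and Section 8.2 extends enrolment only if the primary endpoint is projected to be underpowered.

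It can also be said that the larger figures exaggerate, because the natural candidates are measures of the same weight change. That is partly right. Height is recorded only at Visit 0, so percent change in BMI equals percent change in weight and adds nothing. For such measures the 0.9 row, or less, applies. For appetite or laboratory measures lower correlations are plausible.

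Finally, if interims only project sample size, as Section 8.2 says, the repeated-test figures in step 5 do not apply as they stand. The Summary contradicts Section 8.2 on this, and changing the size on unblinded data still needs a stated method.

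**Conclusion.** The point holds: the sentence has to be replaced in both places, because neither reading is acceptable as written and no other section bounds the error rate. The literal permission to add endpoints is probably unintended.

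The size depends on the reading. With 2 to 6 endpoints at an assumed two-sided 0.05, the chance of at least one false positive runs from 7.0% (two endpoints, correlation 0.9) to 26.5% (six, independent). On the subjects reading it is about 8.3% for two unadjusted tests and about 15.5% for six. These are illustrations, since the plan supplies no alpha, number of endpoints, schedule of looks or boundary from which an actual rate could be derived.

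**What to change.** Replace the sentence in Section 8 and in the Protocol Summary with:

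> The endpoints in 6.1.1 to 6.1.4 are fixed before the first interim look. None will be added or promoted on the basis of trial data, and any measure not listed there (for example %EBWL in 8.1.3) is exploratory, with no significance claim. Longitudinal modelling may inform only the number of subjects needed for the primary effectiveness endpoint, up to 300. If an interim tests the primary endpoint, or the size is changed from unblinded data, the final test will use a pre-specified alpha-spending boundary or combination test that holds the overall two-sided error at 0.05.

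The Summary and Section 8.2 should also be made to agree on whether interims test significance, and the boundary or combination test should be named.

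The cost is small. The sponsor gives up the freedom to add endpoints after seeing data and accepts a stricter threshold if interim tests are kept. For example, equal critical values at 150 and 300 would be 2.178 (nominal two-sided 0.029) in place of 1.96. On the assumptions in 8.2, 75 per group less 30% leaves about 52 evaluable. The expected statistic is then 4/(5·√(2/52)) = 4.08, so power in a single test at 150 goes from Φ(4.08 − 1.96) = 98% to Φ(4.08 − 2.18) = 97%. No visits or measurements change.
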